### **Summary of lapatinib safety**

As of 05-Dec-2011 565 subjects have died due to events reported as serious adverse events (SAEs). One hundred and eleven of these deaths were assessed as related to investigational product (IP) by the investigator; 87 subjects received lapatinib, 13 subjects received comparator, 10 subjects received placebo and 1 subject remained blinded. Based on current exposure, the estimated incidence rate of fatal outcomes related to lapatinib was 0.4% (87/20,586), compared with a rate of 0.3% (23/7421) for subjects who received placebo or comparator. Twenty-one of the lapatinib subjects received lapatinib monotherapy, the remaining 66 received lapatinib in combination with other chemotherapy (including capecitabine, paclitaxel, pazopanib, and trastuzumab). The reported fatal events were all expected events for the cancer treatment regimens and/or the population under study.

The most common adverse events (AEs) in clinical studies, regardless of relationship to study drug, were diarrhea, rash, and nausea. Majority of these AEs were of Grade 1 or 2 severity, and resolved. These events are included in the core safety information (CSI) for lapatinib and are consistent with the safety profile of lapatinib as reported for the program as a whole.

Lapatinib dosed at 750mg twice a day was used in a similar study to this with neoadjuvant delivery followed by craniotomy and tissue removal (NABTC 04-01). There were no safety signals identified associated with wound healing or wound infections. There is no identified experience using pulsatile lapatinib in the setting of any surgery including craniotomy. The safety concerns associated with wound healing or wound infection are unknown with the doses provided with this study.

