After recovery from surgical resection, patients will receive lapatinib post-operatively twice a day for two consecutive days every 7 days (2 days on/5 days off) in 28-day cycles.

Adequate recovery from surgical resection includes, but is not limited to, the following:

- No signs or symptoms of infections related to the surgical wound (*i.e.*, increasing erythema or cellulitis of the surrounding area, large amount of drainage, fever)
- Wound edges have healed

[figure not shown]
Post-operatively, patients must begin treatment within 30 days of surgical resection, and preferably within 3 weeks of the post-operative MRI; if more than 3 weeks elapse after the post-operative MRI, the patient will need a new MRI.

Patients will be followed by routine blood work, general and neurological examination, and MR imaging. See Section [9.1](#) for schedule.

Patients may continue to receive cycles of lapatinib until tumor progression, development of unacceptable toxicity, or meeting other criteria for going off treatment (Section [10.1](#)). Patients will be followed for adverse events for at least 30 days after the last dose of lapatinib. All patients will be followed for survival.

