## 9.0 MONITORING OF PATIENTS

### 9.1 Tables of Required Observations

#### Group A

	Baseline	Pre-Surgery	Day of Surgery	Post-Surgery	Post-Surgery Cycles	Pre-Odd Cycles	Pre-Even Cycles	Every 3 Cycles	Off Treatment (within 7 days)	30-Day Follow-Up
Lapatinib		6			6					
Adverse Event Evaluations			7	10		17	17		12	13
Glucocorticoids Dose	1			19		17			12	
MRI	1			19		17,18			12	
H&P/Neuro exam	1					17	17		12	
KPS	1					17	17		12	
Vital Signs	1,2					2,17	2,17		2,12	
CBC, platelets, Differential	1		11			17	17		12	
Serum Chemistry	1,3		3,14			3,17	3,17		3, 12	
APTT or PTT	1									
Serum Pregnancy Test	1,4									
Echocardiogram	1					16		16		
12-Lead Electrocardiogram	15									
Plasma Pharmacokinetics	8		8							
Fresh Tumor Tissue			9							
Archived Tumor Tissue	5									

- 1 – All baseline measurements must be done within 21 calendar days prior to start of treatment, unless otherwise indicated.
- 2 – Including blood pressure, respiratory rate, heart rate, temperature, weight, and height: height is required at baseline only.
- 3 – Albumin, alkaline phosphatase, total bilirubin, calcium, creatinine, magnesium, phosphorus, potassium, SGOT, SGPT, sodium.
- 4 – Females with child-bearing potential must have a negative serum pregnancy test.
- 5 – Archived tumor tissue from initial surgery at diagnosis of high-grade glioma. See Section [9.5.2](#)
- 6 – Four doses of lapatinib will be administered pre-operatively starting 2 days prior to the day of surgery with the last pre-operative dose taken 3-5 hours prior to scheduled surgery: see Section [4.1](#) for schedule. One additional dose is permitted if unexpected logistical problems delay surgery.  
Post-operatively patients will receive lapatinib twice a day for two consecutive days every 7 days (2 days on/5 days off) in 28-day cycles. Patients are required to keep a pill diary. See Section [4.3.1](#).
- 7 – Patient should be seen on the day of surgery (prior to the the time of surgery) to evaluate for AEs.
- 8 – Plasma specimens for pharmacokinetics will be obtained at baseline and pre- and post-surgical resection. See Section [9.5.3](#) for details.
- 9 – Fresh tumor tissue for correlative studies will be collected day of surgery. See Section [9.5.1](#), [9.5.2](#), and [9.5.4](#) for details.
- 10 – Within 3 days post-surgery.
- 11 – Within minus 1 day

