- 12 – Evaluations done within +7 days of off-treatment date unless indicated; do not repeat: if MRI within 14 days of off-treatment date; if H&P /neuro-exam, KPS, labs within minus 5 days of off-treatment date.
- 13 – Adverse Events must be followed for at least 30 days from the last dose of lapatinib, until resolution, within +14 days.

Drug Distribution and Pharmacodynamic Study of Pulsatile Lapatinib in Surgically Accessible EGFR-Amplified Recurrent High-Grade Glioma

ABTC # 1302

NCI # ABTC-1302

PI: [name]

- 14 – After last dose of study drug, prior to surgery
- 15 – 12-lead electrocardiogram (ECG) must be performed within 2 weeks prior to start of treatment, with QTc  $\leq$ 470 msec.
- 16 – LVEF must be monitored every 12 weeks (3 cycles), including pre-Cycle 1, to ensure that LVEF does not decline below the institutional lower limit of normal. See Section [5.2.2](#).
- 17 – Within minus 5 calendar days of starting cycle
- 18 – For Cycle 1 only, perform scan only if patient will start cycle  $>$ 21 days from post-operative scan (patient must have scan within  $\leq$ 21 days of Cycle 1 start). Record glucocorticoid dose at time of MRI.
- 19 – Perform MRI 1-3 days post-operatively. Record glucocorticoid dose at time of MRI

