Initial safety monitoring: All adverse events will be monitored and collected throughout the trial and documented based on CTCAE version 5.0. If there are three or more delays of scheduled surgery due to lapatinib-related Serious Adverse Events among the initial 8 patients; or if there are any surgical complications and delayed wound healing SAEs grade  $\geq 3$  considered lapatinib-related among the first three patients, ABTC investigators will consult with CTEP investigators and the pharmaceutical sponsor about such events. An internal safety monitoring evaluation will be conducted after the first three patients complete their first follow-up visit after surgery.

Reference Group (for primary PD study):

15 lapatinib-naïve patients with recurrent and surgically accessible EGFR-amplified high-grade glioma will be enrolled as a reference group for the PD evaluation to establish the threshold of 80% reduction in the ratio of pEGFR/total EGFR. After the initial 8 patients are enrolled into Group A, eligible patients will be sequentially assigned to either treatment group or reference group. The sample size of 15 patients on the reference arm yields 90% confidence that the observed median falls between the true 30th and 70th percentiles of the pEGFR/total EGFR distribution for untreated patients.

To avoid batch effect and other variations through tumor sample processing, all tumor samples will be processed at the same time at the [name] Lab, Memorial Sloan-Kettering Cancer Center.

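### The consultation trigger for lapatinib-related surgical and wound-healing SAEs stops after three patients, although all 18 Group A patients carry the same unknown risk

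*Combined protocol and SAP*

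**What the plan says.** Section 2.2 (Summary of lapatinib safety) reports no wound signal in an earlier pre-craniotomy study of 750 mg twice daily. It knows of no experience with the pulsatile regimen around any surgery, and it states: "The safety concerns associated with wound healing or wound infection are unknown with the doses provided with this study".

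Section 11.0 (Initial safety monitoring, under Primary Objectives and Sample Size) sets two consultation triggers, and Section 5.1 repeats them:

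- three or more surgery delays caused by lapatinib-related SAEs among the initial 8 patients;
- "if there are any surgical complications and delayed wound healing SAEs grade" 3 or higher, "considered lapatinib-related among the first three patients".

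The consequence of either is that "ABTC investigators will consult with CTEP investigators and the pharmaceutical sponsor about such events". No pause or stop of enrolment is attached.

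Section 11.0 alone adds a separate step: "An internal safety monitoring evaluation will be conducted after the first three patients complete their first follow-up visit after surgery". It does not define that visit.

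The Group A table in Section 9.1 schedules the first adverse event evaluation after surgery in footnote 10: "Within 3 days post-surgery". The next is the pre-cycle evaluation in footnote 17: "Within minus 5 calendar days of starting cycle". Section 4.1 says: "Post-operatively, patients must begin treatment within 30 days of surgical resection". It lists closure of the wound edges among the conditions for adequate recovery before that treatment.

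**The concern.** The plan identifies one surgical risk as unknown and writes a rule for it, but the rule lapses after the third of 18 patients with the same pre-operative exposure. An identical event in the fourth Group A patient carries no required consultation. The delay trigger beside it covers eight patients. No reason is given for three, and no operating characteristics are stated, whereas the PK and PD rules in the same section have theirs.

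The internal review raises a smaller question. If its reference visit is the evaluation within 3 days of surgery, the review precedes the point at which the protocol itself judges whether the wound has healed.

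At stake is whether a modest excess of wound complications would lead to a required discussion while Group A is still enrolling. The PK and PD inference is not affected.

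**Working it through.** **Plan's own figure.** None is stated for this rule. The neighbouring figures in Section 11.0 do reproduce. For example, the probability of at most 2 successes in 8 is 67.9% at a 25% rate (stated 68%) and 1.13% at a 70% rate (stated 1.1%).

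**Inputs from the documents.** Patients covered: 3 (Sections 5.1 and 11.0). Threshold: any one qualifying SAE. Group A size: 18 (Section 3.1). Patients outside the trigger: 18 − 3 = 15, and 15/18 = 83%.

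**Assumed input.** The true rate p of lapatinib-related grade 3 or higher surgical or wound SAEs per patient is not given. A range of 5% to 30% is shown, with patients treated as independent.

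**Probability that the trigger fires:** 1 − (1 − p)^n. For example, at p = 0.10 and n = 3, 1 − 0.9^3 = 1 − 0.729 = 0.271. At p = 0.20 and n = 3, 1 − 0.8^3 = 1 − 0.512 = 0.488.

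| Assumed p | First 3 | First 8 | All 18 |
|---|---|---|---|
| 5% | 14.3% | 33.7% | 60.3% |
| 10% | 27.1% | 57.0% | 85.0% |
| 20% | 48.8% | 83.2% | 98.2% |
| 30% | 65.7% | 94.2% | 99.8% |

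**Break-even rates for three patients.** The trigger is more likely silent than not when p is below 1 − 0.5^(1/3) = 20.6%. Firing with 80% probability needs p of at least 1 − 0.2^(1/3) = 41.5%.

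**What a clean start shows.** With 0 events in n patients, the one-sided 95% upper bound is 1 − 0.05^(1/n). This is 63.2% for 0 of 3 and 15.3% for 0 of 18.

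**Events only after the third patient.** At p = 0.20, the chance that the first three are event-free and at least two of the next 15 have an event is 0.8^3 × P(Bin(15, 0.2) ≥ 2) = 0.512 × 0.833 = 0.43. No consultation would be required in that case.

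**Timing of the internal review.** Two readings fit the Group A table:

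- *Evaluation within 3 days of surgery.* This is the first scheduled adverse event evaluation after surgery. Its column holds only adverse events, steroid dose and MRI.
- *Pre-Cycle 1 evaluation.* This is the first full examination after surgery. It falls up to 5 days before Cycle 1, which must start within 30 days of resection.

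Under the first reading, suppose that only a share f of eventual events is visible at the review (f is an assumption). The chance that the review sees none in three patients is (1 − p·f)^3. At p = 0.20 this is 0.90^3 = 72.9% for f = 0.5 and 0.95^3 = 85.7% for f = 0.25.

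**The case against.** The strongest case on the other side is that later events are not lost. Section 9.3.3 sends grade 3 to 5 SAEs to the NCI within 24 hours, with a full report 5 calendar days later, and related events more than 30 days after the last dose are also expedited. Section 9.3.4 sends every SAE to the ABTC Central Office within 24 hours. Infection and wound complications have no exception from expedited reporting in Section 9.2.1. Adverse events are collected throughout, and wound healing is a condition of each patient's post-operative treatment. The rule sits under initial monitoring, so a short run-in may be deliberate, and its only consequence is consultation.

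Most of this stands. A reader might infer that an event after the third patient triggers nothing; the reporting sections contradict that. What is missing is narrower: a written duty to consult, including with the pharmaceutical sponsor. Reporting does not fill that gap. If it did, the trigger would not be needed for the first three patients either, and nothing in the documents explains why the fourth differs.

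A reader might also infer that the trigger sees only what is found within 3 days of surgery. The text does not support this. The undefined visit times the internal review alone, and the trigger has no end date for the first three patients. A delayed-healing SAE on day 20 in one of them would still require consultation. Nor is the 3-day evaluation the only one before Cycle 1, since the pre-cycle evaluation is scheduled as well.

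**Conclusion.** The coverage gap holds on the documents' wording: 15 of 18 patients with the same pre-operative exposure fall outside the only surgical and wound trigger, for a risk that the protocol calls unknown. Its size depends on an assumed rate. At 10% and 20%, the trigger fires with probability 27% and 49%, against 85% and 98% if it covered all of Group A.

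It would be tempting to say that the trigger will usually miss the risk. That is true only if the rate is below about 21%, and the documents give no rate.

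The visit timing is an ambiguity rather than an established error. The 3-day reading would be too early for delayed healing, but the pre-Cycle 1 reading is open. On its own it would need only a clarification. The whole point is a cheap improvement to safety monitoring.

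**What to change.** - In Sections 5.1 and 11.0, apply the same consultation-only trigger for lapatinib-related grade 3 or higher surgical-complication and delayed-wound-healing SAEs to all Group A patients.
- In Section 11.0, name the visit meant for the internal review. Keep the early look at acute surgical complications in the first three patients, and state that their wound-healing review is completed at the pre-Cycle 1 evaluation or day 30 after surgery, whichever comes first. The day-30 limit matters because a patient whose wound does not heal may never reach the pre-Cycle 1 evaluation.
- State the trigger's operating characteristics over a range of assumed rates.

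The cost is wording in two sections and more consultations. An any-event rule over 18 patients fires about 60% of the time at a 5% rate (1 − 0.95^18 = 0.603) and about 30% at a 2% rate (1 − 0.98^18 = 0.305). One firing therefore prompts a discussion and is not evidence of an excess. No accrual stop, visit or procedure is added: Section 9.1 already requires adverse event follow-up for at least 30 days after the last dose.

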### **Secondary and Exploratory Objectives:**

1. All treatment or surgically related AEs will be reported descriptively. A proportion of toxicity grade  $\geq 3$  will be estimated using binomial distribution.

2. To estimate inhibition of tumor cell proliferation (KI-67), descriptive statistics will be used for summarizes results and Box plots could be used to present the difference between the treated and untreated groups.
3. To characterize ex-vivo sensitivity of tumor sphere cultures to lapatinib, the *ex-vivo* sensitivity of tumor sphere cultures established from surgical specimens to pulsatile lapatinib is defined by a minimum of 20% reduction in cell proliferation as measured by cell titer glow in the pulsatile lapatinib group compared to the untreated group. Fisher's exact test will be used for testing a difference in the proportion between the two groups.
4. To estimate tumor objective response rate as the evidence of biological activity among patients with recurrent GBM treated by lapatinib, the proportion of patients who had objective PR or CR during the course of the treatment will be estimated along with 95% confidence intervals using the exact binomial method.
5. To estimate overall survival (OS), the survival time is defined from the date of treatment start to the date of death. Patients who have not expired by the data analysis cutoff date will be censored at their last date known to be alive. The Kaplan-Meier method will be used to estimate overall survival probability and median time of survival along with a 95% confidence interval.
6. To estimate progression-free survival, The progression is defined a radiographic tumor progression, a  $\geq 25\%$  increasing from baseline scan with a confirmatory scan at least 8 weeks apart from the initial scan that tumor progression was observed. The date of progression is defined as the date of initial scan deemed tumor progression. The Kaplan-Meier method will be used to estimate progression-free survival probability and median time of survival along with a 95% confidence interval. The progression-free survival at 6-month is defined as: patient, who started treatment, is alive and progression free at the time of 6 month follow-up. The probability of 6-month progression-free survival will be estimated using binomial distribution.

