### Secondary/Exploratory Objectives:

Group A and Reference Group:

1. To evaluate the safety profile of pulsatile lapatinib in pre-operative patients with EGFR amplified recurrent high-grade glioma; to evaluate acute and late toxicities associated with pulsatile lapatinib
2. To determine the effect of lapatinib on tumor cell proliferation (KI-67 staining) (Group A compared to Reference Group)
3. To determine the ex-vivo sensitivity of tumor sphere cultures to lapatinib
4. To assess tumor objective response rate (ORR)
5. To estimate overall survival (OS)
6. To estimate progression-free survival

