## 2.4 Correlative Studies Background

**EGFR gene amplification in tumor cells (Integral):** EGFR mutations in high-grade glioma include point mutations and a variety of structural alterations (Frederick et al. 2000, Frattini et al. 2013, Brennan et al. 2013, Ciriello et al. 2013). Since these mutations are commonly accompanied by amplification of the EGFR gene, evidence of regional DNA amplification of EGFR will be used as an integral biomarker. EGFR amplification will be determined centrally by fluorescence in-situ hybridization (FISH) (See Section [9.5.2](#)).

**Tumor lapatinib concentrations (Integrated):** See Section [2.3](#), above, regarding the rationale and selection of pharmacokinetic endpoints. The concentration of lapatinib in tumor samples will be determined using a validated LC-MS/MS assay. Details of the sample collection, processing, storage and shipment procedures are provided in Section [9.5.5](#).

**EGFR phosphorylation in tumor cells (Integrated):** See Section [2.3](#), above, regarding the rationale and selection of pharmacodynamic endpoints. EGFR phosphorylation will be determined with the mesoscale electroluminescence platform which has shown greater sensitivity than other ELISA-based assays (Sharma J et al. 2012) and is widely used in the evaluation of signal transduction inhibitors (<http://www.mesoscale.com>). Details of the procedures for sample collection, sample batching, and assay performance characteristics are provided in Section [9.5.4](#)., Section [9.5.6](#), and [Appendix IV](#).

**Plasma lapatinib concentrations (Exploratory):** The concentration of lapatinib in plasma samples will be determined using a validated LC-MS/MS assay. Details of the PK sample collection, processing, storage and shipment procedures are provided in Section [9.5.3](#).

**Tumor cell proliferation (KI-67 staining) (Exploratory):** We will compare tumor cell proliferation in lapatinib-treated patients (group A) with tumor cell proliferation in lapatinib-naïve patients (reference group). We will also examine tumor cell proliferation in the archival sample from both groups of patients and compare it to the matched specimen from the current protocol surgery (matched pair comparison). Together, these

analyses aim to determine the effect of lapatinib on tumor cell proliferation. Details of the procedures for sample collection and staining are provided in Section [9.5.2](#).

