### 3.0 PATIENT ELIGIBILITY CRITERIA

#### 3.1 Patient Sample

Sample Size:

Group A: 18 patients

Reference Group: 15 patients

Accrual Rate:

3 patients per month

Gender:

Male and female

Age:

Patients must be at least 18 years of age.

Race/Ethnicity:

Minorities will be actively recruited. No exclusion to this study will be based on race or ethnicity.

Accrual Targets					
Ethnic Category	Sex/Gender				
	Females		Males		Total
Hispanic or Latino	2	+	2	=	4
Not Hispanic or Latino	11	+	18	=	29
Ethnic Category: Total of all subjects	13 (A1)	+	20 (B1)	=	33 (C1)
Racial Category					
American Indian or Alaskan Native	0	+	0	=	0
Asian	2	+	2	=	4
Black or African American	2	+	3	=	5
Native Hawaiian or other Pacific Islander	0	+	0	=	0
White	9	+	15	=	24
Racial Category: Total of all subjects	13 (A2)	+	20 (B2)	=	33 (C2)

(A1 = A2)

(B1 = B2)

(C1 = C2)

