## 9.5 Correlative Studies

Table 9.5: Synopsis of Correlative Studies

Measurement	Technique	Participants	Timing of collection	Collection requirements	More Information
EGFR gene amplification in Tumor: ( Integral Biomarker )	Fluorescence In-Situ Hybridization (FISH) on FFPE	Group A and Reference Group	Archived sample	5 UNSTAINED SLIDES (4 micron thick) from most recent surgery	Section 9.5.2
Ki67 and other IHC measurements ( Exploratory )	IHC of FFPE tumor tissue	Group A and Reference Group	Archived and protocol surgery	20 UNSTAINED SLIDES each from archived tumor block and protocol surgery tumor block: 5 micron thick	Section 9.5.2
Lapatinib blood concentrations ( Exploratory )	LC-MS/MS analysis of plasma samples	Group A	Before and During Protocol surgery	Three BLOOD SAMPLES : one sample collected before starting lapatinib and two samples collected during tumor resection	Section 9.5.3
Lapatinib tumor concentration ( Integrated )	LC-MS/MS analysis of fresh frozen tissue	Group A	Protocol Surgery	Combined Total Tumor Tissue Required for both tumor concentration and EGFR phosphorylation ( FROZEN TUMOR SPECIMEN WILL BE SPLIT INTO ALIQUOTS AT CENTRAL SITE ):	Section 9.5.5
EGFR phosphorylation in Tumor ( Integrated )	Electro-chemiluminescence of fresh frozen tissue	Group A and Reference Group	Protocol surgery	At least 500mg from contrast enhancing region. When possible, also at least 100 mg from non-contrast enhancing region	Section 9.5.6
Ex-vivo sensitivity of tumor sphere cultures ( Exploratory )	Trypan Blue Assay	Group A and Reference Group	Protocol Surgery	When possible, 500 mg or more of additional Tumor Tissue for Tumor Sphere Culture	Section 9.5.7

Biospecimen Criteria for Patient Replacement: patients on protocol will be replaced if any of the following tissue factors apply:

Surgical sample:

- Less than 500 mg of frozen tissue obtained from the contrast enhancing portion of the tumor
- Frozen tissue does not contain tumor
- Time from tumor removal to freezing greater than 5 minutes
- No paraffin tumor block or fewer than 20 unstained slides available.

Archived surgical sample:

- Fewer than 20 unstained slides available

Blood PK (applies to Group A only):

- Blood samples not obtained at time of surgery

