### **9.5.2 Archived and Protocol Surgery Paraffin Tumor Tissue (Group A and Reference Group)**

Prior to registration (Integral Biomarker): Archived tumor tissue from the most recent prior resection of high-grade glioma (pre-treatment) will be collected from all patients who are being screened for enrollment. **Evidence of EGFR amplification from this analysis will be considered a necessary inclusion criteria for enrollment.** EGFR gene amplification must be determined through a CLIA-certified FISH assay. Results of the EGFR-FISH assay must be sent to the ABTC Central Office to confirm patient eligibility. Determination of EGFR gene dosage through next-generation sequencing assay will not suffice for patient eligibility.

After completion of protocol surgery: 20 consecutively cut unstained slides each from the archived sample and the protocol surgery will be requested for exploratory IHC analysis including KI67 Analysis. These can be shipped together in separate containers along with the associated pathology report from the institution of collection. Notification of the delivery must be made by e-mail to both [name] (email: [contact]) and [name] (e-mail: [contact]). Include the name of the courier and the tracking no. in the email.

Please ship to:

[name]  
Memorial Sloan Kettering Cancer Center  
[name]  
[name]  
[name]  
Telephone: + 1 [contact]  
Fax: + 1 [contact]

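### The Ki-67 analysis in Section 11 does not carry forward the archived-to-surgery comparison set out in Section 2.4, so baseline imbalance between non-randomised groups goes unchecked

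*Combined protocol and SAP*

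**What the plan says.** Section 1 words the objective as a comparison between groups: "To determine the effect of lapatinib on tumor cell proliferation (KI-67 staining) (Group A compared to Reference Group").

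Section 2.4 sets out two Ki-67 analyses and says that the two together should show the drug effect. The first is between groups: "We will compare tumor cell proliferation in lapatinib-treated patients (group A) with tumor cell proliferation in lapatinib-naïve patients (reference group"). The second is within patients and covers both groups: "We will also examine tumor cell proliferation in the archival sample from both groups of patients". For each patient, the stated plan for that archived value is to "compare it to the matched specimen from the current protocol surgery (matched pair comparison").

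Section 11, item 2 under the secondary and exploratory objectives, offers descriptive statistics and adds that "Box plots could be used to present the difference between the treated and untreated groups". It mentions no archived value, pairing, change, adjustment or interval.

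The archived material is collected all the same. Section 9.5.2 states that "20 consecutively cut unstained slides each from the archived sample and the protocol surgery will be requested for exploratory IHC analysis including KI67 Analysis". Section 9.5 replaces a patient with "fewer than 20 unstained slides available", a limit applied to the protocol-surgery sample and, separately, to the archived sample.

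On allocation, Section 4.1 puts the first 8 patients in Group A, alternates the next 20 (10 to each group) and puts the last 5 in the Reference Group. Section 3.1 gives the totals: "Group A: 18 patients", and 15 in the Reference Group.

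**The concern.** The objective concerns a drug effect, and the only planned contrast compares two groups that were not randomised. Thirteen of the 33 patients (8 + 5) enter in single-group blocks at opposite ends of accrual. Section 3.2 admits WHO grade III and IV tumours after any number of earlier regimens, so the groups could differ in proliferation before any lapatinib is given. Archived Ki-67 is the only measure of proliferation before lapatinib that is collected for each patient, and Section 11 gives it no role.

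A difference in surgery Ki-67 could then reflect the drug, case mix or both, and the planned output could not help to tell them apart. Patients can also be replaced for lacking archived slides whose use for Ki-67 the analysis section never describes. If the analysis is left open until the data are in, the choice among the raw difference, the change and the adjusted difference becomes post hoc.

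**Working it through.** **Reading the sections together.** Section 2.4 names two comparisons. Section 11 names one, by way of the optional box plots. Section 1 matches Section 11. Section 2.4 is current text, so the paired comparison is promised but not specified in the place where analyses are defined.

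**Which archived specimen.** Eligibility criterion 7 (Section 3.2) and note 5 to both tables in Section 9.1 point to tissue from the first surgery at diagnosis. Section 9.5.2 points to the latest earlier resection, labelled as pre-treatment. For a patient with more than one earlier resection these can be different specimens.

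**Inputs for the size.** Group sizes are 18 and 15 (Section 3.1). The plan states no SD, effect size, power or test for Ki-67, so it has no figure to reproduce. I set the SD to 1 at both time points and take r, the archived-to-surgery correlation, as an assumption over a range.

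**Formulas** for the SE of the Group A minus Reference difference:
- Unadjusted: sqrt(1/18 + 1/15) = sqrt(0.1222) = 0.350 SD.
- Difference in change scores: 0.350 × sqrt(2(1 − r)).
- Adjusted for archived Ki-67 (ANCOVA): 0.350 × sqrt((1 − r²)(1 + 1/29)). Here 29 = 18 + 15 − 4, and the factor is the average cost of estimating the slope when the covariate has the same distribution in both groups.
- Effective sample gain from adjustment: 1/[(1 − r²)(30/29)] − 1.

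| Assumed r | Change-score SE | Adjusted SE | Adjusted versus unadjusted SE | Effective sample gain |
|---|---|---|---|---|
| 0 | 0.494 | 0.356 | +2% | −3% |
| 0.3 | 0.414 | 0.339 | −3% | +6% |
| 0.5 | 0.350 | 0.308 | −12% | +29% |
| 0.6 | 0.313 | 0.284 | −19% | +51% |

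For example, at r = 0.5: 0.75 × 30/29 = 0.776, and 1/0.776 = 1.29.

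Adjustment breaks even where 1 − r² = 29/30, that is r = sqrt(1/30) = 0.18. Change scores break even only at r = 0.5. Simulation with 20,000 trials per value gave adjusted SEs of 0.356, 0.340 and 0.308 at r = 0, 0.3 and 0.5, in agreement with the formula.

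**Imbalance.** If the groups differ by D SDs in archived Ki-67, the part of the unadjusted contrast that archived Ki-67 predicts is r × D. A chance imbalance of one SE (D = 0.350) gives 0.3 × 0.350 = 0.105, 0.5 × 0.350 = 0.175 or 0.6 × 0.350 = 0.210 SD. Sequential filling could make D larger. Reporting archived Ki-67 by group shows D whatever r is.

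**The case against.** The strongest reply is that Ki-67 is labelled exploratory, with no test, power claim or decision rule. Descriptive statistics can include a paired summary, Section 2.4 still stands, and an adjusted model for such an endpoint may be seen as analyst preference. The archived slides also serve other immunohistochemistry, so they are not collected for this comparison alone. All of that is correct, and it keeps the point small. It does not supply an analysis for the promised comparison or a check on imbalance.

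Four stronger readings are tempting, and the documents do not support them:
- A reader might infer that the archived data are discarded. They are still collected and Section 2.4 still promises to examine them; Section 11 is silent.
- A reader might infer that the planned contrast is simply less precise. For ANCOVA that needs r above about 0.18. For change scores, the closest match to a matched-pair comparison, it needs r above 0.5; at r = 0.3 the change-score SE is 18% larger than the unadjusted one. Low r is plausible, since radiation, with or without chemotherapy, comes before recurrence.
- A reader might treat archived Ki-67 as a true baseline at recurrence. Under the diagnosis-specimen definition it predates radiation, so it is an imperfect proxy.
- A reader might take the paired plan as confined to Group A, where change without drug could not be separated out. Section 2.4 covers both groups.

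In the other direction, one sentence in Section 7.3 refers to a randomisation assignment. No randomisation procedure is described, and Sections 4.1 and 11 both describe sequential assignment.

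**Conclusion.** The point holds as a low-severity improvement. Section 11 leaves the archived-to-surgery comparison unspecified, and its unadjusted contrast cannot show or correct imbalance in pre-lapatinib proliferation between sequentially filled groups.

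The gain from adjustment is conditional. It ranges from a 3% loss of effective sample size at r = 0 to a 51% gain at r = 0.6, and the documents do not say where r lies. These figures assume equal SDs, a linear relation on the analysis scale and similar covariate distributions in the two groups; a marked imbalance would widen the adjusted interval. Removal of bias rests on the same correlation, so adjustment may remove only part of any imbalance. The case for the change is therefore mainly transparency about baseline and a method fixed in advance, with precision as a possible extra. The primary PK and PD analyses do not use Ki-67 and are unaffected.

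**What to change.** 1. Reconcile Sections 3.2, 9.1 and 9.5.2 so that one archived specimen, defined the same way for every patient, supplies the Ki-67 value.
2. In Section 11, item 2, report archived Ki-67 and the within-patient archived-to-surgery change by group, as description only.
3. In the same item, estimate the Group A minus Reference difference in surgery Ki-67 (log or logit scale, chosen beforehand) by a linear model with group and archived Ki-67. Give a 95% confidence interval next to the box plots, and note that the archived value is an imperfect baseline.

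If the sponsor does not want this analysis, the alternative is to remove the matched-pair statement from Section 2.4 and reconsider the archived-slide replacement rule.

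The cost is a wording change and one regression, with no new tissue. The statistical downside is about 2% in SE if the correlation is zero. The change should be made before Ki-67 results are seen.
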